#### 6 STUDY ASSESSMENTS AND PROCEDURES

#### 6.1 Schedule of Assessments

The efficacy and safety assessments for this study are presented in Appendix A: Schedule of Assessments.

#### 6.2 Study Visits

#### 6.2.1 Screening

This study will have no formal screening.

Subjects who meet all inclusion/exclusion criteria and sign the ICF will be enrolled in the study.

#### 6.2.2 Baseline Visit

Subjects will be evaluated to determine if they meet all inclusion/exclusion criteria. Those signing the ICF will be enrolled in the study.

Note: If the subject was in LTFU in Study KD025-208 or in Study KD025-213, the subject will only have LTFU assessments performed once approximately every 3 months (Section 6.2.5).

Belumosudil will be administered as follows:

- Subject receives same dose of belumosudil as assigned in Study KD025-208 or in Study KD025-213, as appropriate. The first dose may be taken at home or in the clinic.
- Dispense a study drug diary to the subject

The following data will need to be captured from Study KD025-208 or Study KD025-213:

- The dosing group to which the subject was assigned or randomized
- Clinician-reported Global cGVHD Activity Assessment from Day 1
- Any ongoing AEs

The following efficacy assessments will be performed:

Clinician-reported Global cGVHD Activity Assessment

- Response assessment. (Note: all responses will be assessed with respect to Cycle 1 Day 1 of Study KD025-208 or Study KD025-213.)
- PFT (for subjects with lung cGVHD or when lung cGVHD is suspected)
- LSS
- Use of corticosteroid dosage
- Use of other cGVHD therapies

The following safety assessments will be performed:

- Symptom-directed PE
- Vital signs
- Weight and height
- KPS
- Hematology lab testing
- Clinical chemistry lab testing
- 12-lead ECG
- Urine pregnancy test (any positive results will be confirmed with serum testing)
- Use of concomitant medications
- AEs

### 6.2.3 Month 3 Visit and Every 3 Month Visits Thereafter (± 14 days)

Three months ( $\pm$  14 days) after Baseline, subjects will have the following procedures/assessments:

- Collection of any remaining belumosudil from subject
- Dispensing belumosudil medication at the same dose. Doses may be taken at home or in the clinic.
- Collection of study drug diary
- Dispensing new study drug diary
- Clinician-reported Global cGVHD Activity assessment

- Response assessment
- PFT\*
- LSS
- Use of corticosteroid dosage
- Use of other cGVHD therapies
- Symptom-directed PE
- Vital signs
- Weight
- KPS
- Hematology lab testing
- Clinical chemistry lab testing
- 12-lead ECG
- Urine pregnancy test (any positive results will be confirmed with serum testing)
- Use of concomitant medications
- AEs
- \* When performing PFT, the same equipment and tester should be used during the course of the study when possible. The PFTs should be conducted in accordance with study guidelines and the American Thoracic Society/European Respiratory Society standardization of lung function testing.

### 6.2.4 28 Day Follow-Up Visit

This 28-day Follow-up Visit (± 7 days) will be 28 days after the last dose of belumosudil.

Subjects will have the following assessments and procedures:

- Collection of any remaining belumosudil from subject
- Collection of study drug diary
- Use of corticosteroid dosage
- Use of other cGVHD therapies

- Symptom-directed PE
- Vital signs
- Weight
- KPS
- Hematology lab testing
- Clinical chemistry lab testing
- 12-lead ECG
- Urine pregnancy test (any positive results will be confirmed with serum testing)
- Use of concomitant medications
- AEs

### 6.2.5 Long-term Follow-up

Long-term Follow-up will start at Baseline for enrolled subjects who have been permanently discontinued from belumosudil in Study KD025-208 or in Study KD025-213 where they have not yet had an FFS event. The LTFU will occur after the 28-day Follow-up Visit has been completed for enrolled subjects who were actively dosed with belumosudil at Baseline.

Subjects will have LTFU approximately every 3 months until an FFS event occurs. This LTFU assessment will occur by subjects being contacted by telephone, e-mail, or postal mail to confirm survival status, any initiation of new systemic cGVHD therapies, and relapse of underlying disease. Alternatively, this information may be obtained from the subject's medical records.

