	been completed, subjects will have LTFU approximately every 3 months until a failure-free survival (FFS) event occurs. This LTFU assessment will occur by subjects being contacted by telephone, e-mail, or postal mail to confirm survival status, any initiation of new systemic cGVHD therapies, and relapse of underlying disease. Alternatively, this information may be obtained from the subject's medical records.
Number of Study Centers	Approximately 20
Number of Subjects	Approximately 70
Approximate Duration of Subject Participation	Subjects may receive belumosudil up to an additional 2 years beyond what they had received in Study KD025-208 or Study KD025-213, at the discretion of the Investigator and with guidance from the medical monitor.  Subjects will be treated with belumosudil until cGVHD progression or
	unacceptable toxicity.  Subjects will return to the clinic for a 28-day Follow-up Visit at 28 days (± 7 days) after the last dose of study drug. Subjects will have LTFU approximately every 3 months until a FFS event occurs. After the 28-day Follow-up Visit has been completed, subjects will be contacted approximately every 3 months by telephone, e-mail, or postal mail to confirm survival status, any initiation of new systemic cGVHD therapies, and relapse of underlying disease.
Study Treatment	Belumosudil will be administered orally at the same dose the subject received in Study KD025-208 or in Study KD025-213.
	Subjects will be provided with an adequate supply of belumosudil. Study drug accounting will be performed at each visit.
Criteria for Inclusion and Exclusion	Inclusion Criteria:  1. Subjects must have been treated with belumosudil for at least 1 of the following:

- a. Actively receiving belumosudil on Study KD025-208 or Study KD025-213 (excluding adults in the Companion Study and excluding adolescents enrolled under KD025-213 Amendment 2 [01 June 2020]).
  b. Is in Long-term Follow-up (LFTU) on Study KD025-208 or
- b. Is in Long-term Follow-up (LFTU) on Study KD025-208 or Study KD025-213. Long-term Follow-up will be defined as the period after ending treatment with belumosudil and until a FFS event occurs.
- Adult enrolled in the Companion Study under KD025-213 Amendment 2 (01 June 2020) and has received at least 6 months of treatment of belumosudil or is in LTFU

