#### 4.3 Inclusion Criteria

- 1. Subjects must have been treated with belumosudil for at least 1 of the following criteria:
  - Actively receiving belumosudil on Study KD025-208 or on Study KD025-213 (excluding adults in the Companion Study and excluding adolescents enrolled under KD025-213 Amendment 2 [01 June 2020])
  - b. Is in LTFU on Study KD025-208 or on KD025-213. Long-term Follow-up will be defined as the period after ending treatment with belumosudil and until an FFS event occurs.
  - c. Adult enrolled in the Companion Study under KD025-213 Amendment 2
     (01 June 2020) who has received at least 6 months of treatment of belumosudil or is in long-term follow-up
- 2. Female subjects of childbearing potential have a negative pregnancy test at enrollment. Females of childbearing potential are defined as sexually mature females without prior hysterectomy or who have had any evidence of menses in the past 12 months. However, females who have been amenorrheic for 12 or more months are still considered to be of childbearing potential if the amenorrhea is possibly due to prior chemotherapy, anti-estrogens, or ovarian suppression.
- 3. Sexually active females of childbearing potential enrolled in the study must agree to use 2 forms of accepted methods of contraception during the course of the study and for 3 months after their last dose of study drug. Effective birth control includes:
  - a. Intrauterine device plus 1 barrier method
  - Stable doses of hormonal contraception for at least 3 months (e.g., oral, injectable, implant, transdermal) plus 1 barrier method

- 2 barrier methods. Effective barrier methods are male or female condoms, diaphragms, and spermicides (creams or gels that contain a chemical to kill sperm) or
- d. A vasectomized partner
- 4. For male subjects who are sexually active and who are partners of females of childbearing potential: agreement to use 2 forms of contraception and to not donate sperm during the treatment period and for at least 3 months after the last dose of study drug.
- Subject (or the subject's legally authorized representative) is able to provide written informed consent prior to the performance of any study-specific procedures.
- 6. It is in the best interest of the subject to participate in the study.

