### 6.3 Efficacy Endpoints

The efficacy endpoints of this study will be:

- Duration of Response (DOR)
- Change in LSS (Appendix D: Lee cGVHD Symptom Score)

- Time to Next Treatment (TTNT): defined as the time from the first dose of belumosudil to the start of additional systemic cGVHD therapy
- FFS: defined as the absence of cGVHD treatment change, non-relapse mortality, and recurrent malignancy
- Overall Survival (OS): defined as the time from first dose of belumosudil to the date of death due to any cause
- Percentage of subjects who have a best response of CR and percentage of subjects who have a best response of PR
- Response by individual organ
- Change in corticosteroid dose: the change in prednisone equivalent dose of corticosteroids (mg/kg/day) during the study
- Change in cGVHD Global Severity Rating using the Clinician-reported Global cGVHD Activity Assessment (Appendix B: Clinician-reported Global cGVHD Activity Assessment)

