(Height is only required at Baseline.) The study drug diaries for the past 3 months will be collected, and new study drug diaries dispensed. Any remaining belumosudil will be collected. Subjects may receive belumosudil on Study KD025-217 for up to an additional 2 years, at the discretion of the Investigator (and with guidance from the medical monitor), beyond what they had received in Study KD025-208 or Study KD025-213, cGVHD progression, or unacceptable toxicity.

Subjects will return to the clinic for a 28-day Follow-up Visit at 28 days (± 7 days) after the last dose of study drug. Subjects will have LFTU approximately every 3 months until an FFS event occurs. After the 28-day Follow-up Visit has been completed, subjects will be contacted approximately every 3 months by telephone, e-mail, or postal mail to confirm survival status, any initiation of new systemic cGVHD therapies, and relapse of underlying disease. Alternatively, this information may be obtained from the subject's medical records.

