3.7.2.4 Failure-free-survival (FFS)

FFS is defined as the absence of new cGVHD systemic therapy, non-relapse mortality and recurrent malignancy (i.e., underlying disease) and is censored by last response assessment or long term follow up assessment, whichever is the latest and available. Kaplan-Meier plots, descriptive statistics of FFS and landmark FFS at 6, 12, 18, 24, 30 and 36 months will be provided. In addition, analyses for the three components of FFS will also be provided.

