3.7.2.5 Overall Survival (OS)

OS is defined as time from first dose of belumosudil to the date of death due to any cause and is censored by last response assessment or long term follow up assessment, whichever is the latest and available. Kaplan-Meier plots, descriptive statistics of OS and landmark OS at 6, 12, 18, 24, 30, 36 months will be provided.

3.7.2.6 Percentage of subjects who have a best response of PR and percentage of subjects who have a best response of CR

The percentage of subjects who have a best response of PR and percentage of subjects who have a best response of CR will be summarized separately by treatment groups.

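### Survival follow-up after a non-fatal FFS event is not clearly specified, so OS can be censored around a potentially prognostic failure and later deaths missed

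*Protocol*

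**What the plan says.** **When follow-up stops.** Protocol 6.2.5: "Subjects will have LTFU approximately every 3 months until an FFS event occurs". The Synopsis ("subjects will have LTFU approximately every 3 months until a failure-free survival (FFS) event occurs") and SAP 2.2 ("Subjects will have LFTU approximately every 3 months until an FFS event occurs") give the same stop. Protocol 4.3 builds it into the definition of the period: "Long-term Follow-up will be defined as the period after ending treatment with belumosudil and until an FFS event occurs".

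**What counts as an FFS event.** In Protocol 6.3, FFS is "defined as the absence of cGVHD treatment change, non-relapse mortality, and recurrent malignancy". SAP 3.7.2.4 narrows the first component: "FFS is defined as the absence of new cGVHD systemic therapy, non-relapse mortality and recurrent malignancy". In both, two of the three components are non-fatal.

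**How OS is defined and censored.** In Protocol 6.3, OS is "defined as the time from first dose of belumosudil to the date of death due to any cause". Under SAP 3.7.2.5 it "is censored by last response assessment or long term follow up assessment, whichever is the latest and available". The SAP plans Kaplan-Meier plots and landmarks at 6, 12, 18, 24, 30 and 36 months.

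**Contact sentences with no stated end.** Protocol 3.1 and 3.2, the duration row of the Synopsis, the Appendix A note and SAP 2.2 also describe remote contact about survival after the 28-day visit. Those sentences do not name a stopping point of their own. None says that contact goes on after an FFS event.

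**The concern.** Kaplan-Meier estimation of OS treats a censored subject as having the same future risk of death as those still followed. Here scheduled follow-up can end because the subject has failed treatment or relapsed, and either may change the risk of death. If mortality is higher after failure and later deaths go uncollected, the OS curve mostly describes subjects who have not failed, and it is too favourable.

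One class of death is especially exposed. FFS counts only non-relapse mortality, so a death after relapse always follows an FFS event. Among off-drug subjects, such deaths would be found mainly when relapse and death fall between two contacts.

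Survival status that was never collected cannot be recovered at the analysis stage.

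**Working it through.** The documents give no figure for OS or for mortality after failure, so there is nothing to reproduce. The check traces each type of subject through the text, then illustrates the size under stated assumptions.

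**1. Subjects who stop drug because of a non-fatal failure.** Progression needing new systemic therapy and histologic recurrence both end treatment (Protocol 4.6, 4.8), and with it the 3-monthly response visits (6.2.3). The 28-day visit has no response assessment (6.2.4; Appendix A, Table 7), and LTFU has already met its end point. The last qualifying date can therefore be the 3-monthly visit before the failure.

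**2. Subjects already off drug.** They have LTFU contacts only (6.2.2, 6.2.5). The contact that detects new therapy or relapse comes after the event, by up to about 3 months, and is normally the OS censoring date.

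**3. Subjects who stay on drug after an event that the SAP counts as failure.** An example is the corticosteroid increase that SAP 3.7.2.8 counts as new systemic therapy. They keep their response visits and are not affected at that event.

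**4. Other routes to a death.** Protocol 7.3.5.1 and 7.3.5.2 require reports of deaths on drug or within 28 days of it, and afterwards only of drug-related SAEs. Public data are mentioned only after withdrawal of consent (4.6).

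**5. Which landmarks are open.** Assume entry near 08 September 2021, the date of the amendment cited in SAP section 1. That is 567 days, or 18.6 months, after the 19 February 2020 cutoff.
- KD025-213 median: 7.9 + 18.6 = 26.5 months, leaving (36 − 26.5)/12 ≈ 0.8 year before month 36.
- Last main-cohort KD025-213 subject (cutoff 6 months after that first visit): 6 + 18.6 = 24.6 months.
- KD025-208 median: 28.8 + 18.6 = 47.4 months, already past month 36.
- Companion Study adults (Amendment 2, 01 June 2020): at most 464 days, or 15.2 months, leaving at least (36 − 15.2)/12 ≈ 1.7 years.

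**6. Illustrative size.** All rates are assumptions. Event-free subjects die at rate h0 = 0.05 per year or fail non-fatally at rate f = 0.15 to 0.30 per year. After failure they die at h0 × HR. Every failure loses follow-up, and the clock starts at entry.
- OS censored at failure: exp(−h0·t)
- True OS: exp(−(h0+f)t) + f[exp(−h0·HR·t) − exp(−(h0+f)t)]/(h0 + f − h0·HR)

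Example with t = 0.75, f = 0.30, HR = 5: censored OS = exp(−0.0375) = 0.9632. True OS = 0.7691 + 0.30 × (0.8290 − 0.7691)/0.10 = 0.9488. The difference is 1.44 points.

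Overstatement of OS in percentage points (negative = understated):

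| Years at risk | f | HR 0.5 | HR 1 | HR 2 | HR 5 |
|---|---|---|---|---|---|
| 0.75 | 0.15 | −0.10 | 0 | 0.19 | 0.74 |
| 0.75 | 0.30 | −0.19 | 0 | 0.37 | 1.44 |
| 1 | 0.15 | −0.17 | 0 | 0.33 | 1.27 |
| 1 | 0.30 | −0.33 | 0 | 0.64 | 2.42 |
| 2 | 0.15 | −0.63 | 0 | 1.19 | 4.31 |
| 2 | 0.30 | −1.14 | 0 | 2.17 | 7.84 |

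At 0.75 year and HR 2 to 5, the same formula gives 0.10 to 0.75 points with h0 halved to 0.025, and 0.37 to 2.63 with h0 doubled to 0.10.

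Two variants were simulated with 2 million subjects at h0 = 0.05 and 0.75 year. If a random half of failures lose follow-up, the overstatement is 0.09 to 0.66. If all later deaths become known but survivors stay censored at failure, OS is understated by 0.22 to 0.59.

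**7. Sampling error for scale.** With 70 subjects and OS of 80 to 90% (assumed), the 95% half-width is 1.96·√(S(1−S)/70): 9.4 points at 80% and 7.0 at 90%.

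**The case against.** **Contact may continue.** The open-ended contact sentences can be read as survival contact that does not stop at failure. This stands in part: the text is ambiguous, and a reader who infers that all survival contact certainly ends at failure goes further than it allows. The stop is still the better reading. In 3.1, 3.2 and SAP 2.2 the contact sentence directly follows the FFS stop, 6.2.5 describes one process with one end, and 4.3 defines the period as ending there.

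**Censoring is not always at or before the failure.** A reader might infer that it is for everyone. The documents do not support that. Off-drug subjects are normally censored after the event, and those who remain on drug continue to be assessed.

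**Stopping drug is not leaving the study.** The first sentence of Protocol 4.6 governs how long belumosudil is given. This is correct, but once drug stops only the 28-day visit and LTFU remain, and LTFU ends at the failure. Protocol 7.3.1 counts deaths while a subject is on study, but does not say whether that status lasts after LTFU ends.

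**The effect is small and the study descriptive.** There is no hypothesis (9.1) and no power calculation (9.2), and OS is one of nine secondary items (SAP 2.1.2). At the horizon relevant to most subjects the illustrated bias is well inside sampling error. This stands and limits the importance. It does not remove the point, because missing survival status is cheap to collect now and cannot be reconstructed later.

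**Conclusion.** The point holds as a modest one. The plan does not clearly provide survival follow-up after a non-fatal FFS event, so following it can tie OS censoring to prognosis and leave later deaths uncollected.

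The direction depends on mortality after failure, which the documents do not give. OS is likely optimistic if mortality rises and unbiased if it is unchanged. It is understated if mortality falls, or if deaths are learned by chance while survivors are not updated. With h0 = 0.05 per year, f = 0.15 to 0.30 per year, HR 2 to 5 and all failures lost, the overstatement is about 0.2 to 1.4 points over 0.75 year.

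A reader might infer a bias of several points across the whole OS curve. The documents do not support that. On the assumed entry date, the 6- to 24-month landmarks have passed for main-cohort subjects, so the issue mainly concerns months 30 and 36 and the Kaplan-Meier tail. The 2-year rows of the table lie mostly beyond the listed landmarks for that cohort. Companion Study adults, 20 of whom were planned (Protocol 1.4.2), could be affected at earlier landmarks.

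**What to change.** **Protocol** (Synopsis, 3.1, 3.2, 6.2.5 and the Appendix A note): state that a survival-status-only contact or medical-record check continues after a non-fatal FFS event until death, withdrawal or study end. At minimum, do one vital-status sweep of all enrolled subjects before each data cut.

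**SAP 3.7.2.5:** censor OS at the last date known alive. Apply this only together with the systematic check, so that deaths are not updated while survivors are left at their failure date.

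**If neither is done:** report OS as having survival follow-up that ends at failure, and state the limitation.

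**Cost:** a short amendment with IRB/IEC approval (Protocol 13) at about 20 sites, one SAP sentence, minor eCRF and possibly consent changes, and re-contact or record checks for subjects whose LTFU has already ended. No clinic visits are added, and 6.2.5 already allows remote contact and medical records. The KD025-208 summary (Protocol 1.4.1) describes survival contact about every 8 weeks with no stop at failure, which suggests that this is feasible.

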### 6.2.6 Unscheduled Visit

The assessments and procedures performed at any unscheduled visit will depend on the clinical judgment of the Investigator.

### 6.3 Efficacy Endpoints

The efficacy endpoints of this study will be:

- Duration of Response (DOR)
- Change in LSS (Appendix D: Lee cGVHD Symptom Score)

- Time to Next Treatment (TTNT): defined as the time from the first dose of belumosudil to the start of additional systemic cGVHD therapy
- FFS: defined as the absence of cGVHD treatment change, non-relapse mortality, and recurrent malignancy
- Overall Survival (OS): defined as the time from first dose of belumosudil to the date of death due to any cause
- Percentage of subjects who have a best response of CR and percentage of subjects who have a best response of PR
- Response by individual organ
- Change in corticosteroid dose: the change in prednisone equivalent dose of corticosteroids (mg/kg/day) during the study
- Change in cGVHD Global Severity Rating using the Clinician-reported Global cGVHD Activity Assessment (Appendix B: Clinician-reported Global cGVHD Activity Assessment)

# 6.4 Safety Endpoints

The follow-up safety endpoints of this study will be obtained at regular intervals and will include:

- AEs
- Grade ≥ 3 AEs
- SAEs
- Deaths
- PEs
- Vital signs
- Clinical laboratory evaluations
  - Hematologic: white blood cell count with differential, red blood cell count, hemoglobin, hematocrit, platelet count, and mean corpuscular volume
  - Serum chemistry: albumin, alkaline phosphatase, ALT, AST, blood urea nitrogen, Ca, Cl, CO2, creatinine/glomerular filtration rate (Appendix F:

Equations to Predict Glomerular Filtration Rate (MDRD-4), creatinine phosphokinase, total and direct bilirubin, gamma glutamyl transferase, globulin, glucose, lactate dehydrogenase, Mg, P, K, Na, total protein, and uric acid

 Pregnancy testing: urine pregnancy tests will be done in females of childbearing potential. Positive urine results will be confirmed with serum testing. If pregnancy is confirmed with serum testing, belumosudil will be discontinued.

